### **1.3.2 Secondary and exploratory objectives**

Secondary objectives:

- 1) Examine the difference in the proportion of participants that achieves an 8-point improvement in their ISI-score between inpatient multidisciplinary rehabilitation + dCBT-I (intervention group) and inpatient multidisciplinary rehabilitation only (control group), 3-, 6-, and 12 months after end of rehabilitation.
- 2) Evaluate the effectiveness of the intervention on pain intensity, fatigue, health-related quality of life, physical function, and physical activity at 3-, 6-, and 12 months after end of rehabilitation.
- 3) Evaluate the long-term effectiveness of the intervention on sickness absence and use of prescribed sleep and pain medication during 12 months of follow-up after rehabilitation (this will be done if successful register linkage within the time frame of the project).

If the data material allows it, it will be relevant to examine the following exploratory objectives:

- 4) Explore whether changes in pain intensity and fatigue mediate the effect of dCBT-I on insomnia severity.
- 5) Explore whether sex, age, symptoms of anxiety and depression, pain intensity and level of physical activity at baseline moderate the effect of dCBT-I on insomnia severity and secondary outcomes (pain intensity, health-related quality of life, sickness absence and use of prescription sleep and pain medication).

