### **2.2 Randomization and treatment assignment**

The randomization will be at group level to avoid contamination between members of the same rehabilitation group. Each group are randomized using a computer-generated block randomization provided by the Clinical Research Unit (Project support) at the Faculty of Medicine and Health Sciences at the Norwegian University of Science and Technology (third party).

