### 2.3 Determination of sample size

We anticipated that around five of 10 patients will have insomnia within each rehabilitation group and that the average Insomnia Severity Index (ISI)-score for participants completing usual treatment will be 15 ( $SD = 4$ ). An average 4-point improvement on the ISI score is considered a meaningful change. In order to maximize the number of participants receiving the additional treatment (dCBT-I), we will randomize the participants to the intervention and usual care at a ratio of 2:1. Recruiting 15 clusters with 2:1 randomization will achieve 80% power to detect a 4-point difference between the intervention and usual treatment group, with a conservative assumption that the intraclass correlation is 0.2 and the coefficient of variation in cluster size up to 0.7, and with a significance level of 5%. This would mean that around 150 participants will be screened to give an expected sample size of 75 (50 in dCBT-I + usual care and 25 in usual care). We expect a dropout rate of approximately 20% and that around 50% of the participants in the intervention group will complete at least four of the dCBT-I modules. Given that the per-protocol analysis is of particular interest in this study, we aim to recruit 21 clusters to account for the fact that we expect an average of four participants per cluster in the control group to complete the follow-up, and an average of two participants in the intervention group to complete at least four of the modules and attend the follow-up.

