#### 5.1.2 Secondary outcomes

- 1) Difference in the proportion of participants that achieves an 8-point improvement on ISI between the intervention group and the control group. This is in accordance with the literature suggesting an improvement of the ISI score  $\geq 8$  points is a meaningful improvement, indicating that the intervention has a positive impact on the individual’s sleep [2].
- 2) The effect of the intervention on
  - a. pain intensity measured using a visual analogue scale from 0 to 100.
  - b. fatigue measured using a visual analogue scale from 0 to 100.
  - c. health-related quality of life measured by EQ-5D.
  - d. physical function measured by PSFS.
  - e. physical activity measured by three questions about frequency, duration and intensity of physical activity per week

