## 5.3 Analysis of secondary outcomes

For binary secondary outcomes (e.g., clinically relevant change in ISI, minimal important change in PSFS), we will use a generalized estimated equation logistic model to estimate the odds ratio (OR) for achieving at least an 8-point improvement in ISI score. In these analyses, we will assume an exchangeable correlation structure and a robust variance estimator. For the other secondary outcomes, a mixed linear regression model will be used.

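### The ISI responder GEE does not name its clustering unit or a small-sample correction for about 21 randomised groups, and it estimates an odds ratio where the outcome is a difference in proportions

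*SAP*

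**What the plan says.** - **Model (SAP 5.3).** Binary secondary outcomes get a logistic GEE "to estimate the odds ratio (OR) for achieving at least an 8-point improvement in ISI score", for which "we will assume an exchangeable correlation structure and a robust variance estimator". No cluster variable, small-sample correction or reference distribution is given.
- **Outcome (SAP 1.3.2 and 5.1.2).** The objective is worded "Examine the difference in the proportion of participants that achieves an 8-point improvement in their ISI-score", at 3, 6 and 12 months. The outcome is worded "Difference in the proportion of participants that achieves an 8-point improvement on ISI between the intervention group and the control group".
- **Randomised unit (SAP 2.2).** "The randomization will be at group level to avoid contamination between members of the same rehabilitation group".
- **Size and planning values (SAP 2.3).** "we aim to recruit 21 clusters", allocated 2:1. The power statement is made "with a conservative assumption that the intraclass correlation is 0.2 and the coefficient of variation in cluster size up to 0.7", and "around five of 10 patients will have insomnia within each rehabilitation group". About 20% dropout is expected.
- **Where group is modelled (SAP 5.2.1).** Rehabilitation group appears only as a third level in a sensitivity analysis of the linear mixed model. The SAP says there that it does not expect strong group effects.
- **Advance publication (SAP 3.4.2).** Code for the main analyses is to be published before they are run. The SAP does not say whether that includes the responder analysis.

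**The concern.** In a GEE the choice of cluster decides what the exchangeable correlation describes and what the robust variance protects against. Section 5.3 leaves that choice open between two units:

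- **Participant.** The GEE handles the repeated visits but treats members of the same randomised group as independent.
- **Rehabilitation group.** The GEE follows the randomisation, but the robust variance then rests on about 21 units, 7 of them in the control arm. An uncorrected sandwich variance is biased downwards with so few units.

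The group-level sensitivity analysis in 5.2.1 does not reach this model, so the responder outcome has no stated group-level analysis at all. If the unit stays open, it could also be chosen after the results are seen.

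The effect measure is a separate matter. The quantity named in the objective would have neither an estimate nor an interval. At stake are the width of the confidence interval and the reported size of effect for the first-listed secondary outcome.

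**Working it through.** **1. Inputs from SAP 2.3.** 21 groups at 2:1 gives 14 vs 7. About 5 eligible patients per group, ISI SD 4, ICC 0.2, size CV up to 0.7, dropout about 20%, significance level 5%; SAP 2.4 makes tests two-sided. Assumed, because the SAP gives no figure: 30% responders, the within-person correlation between visits, and that the ISI-score ICC carries over to ISI improvement.

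**2. The plan's own figure.** The SAP states no power for the responder outcome. For continuous ISI it states 80% with 15 clusters (25 vs 50 participants).
- L = 5(0.2)/(5(0.2)+0.8) = 0.556.
- Design effect = (1+4(0.2))/(1-0.49 x 0.556 x 0.444) = 2.048.
- Effective sizes are 25/2.048 = 12.2 and 50/2.048 = 24.4.
- SE = 4 x sqrt(1/12.2+1/24.4) = 1.402.
- Power = Phi(4/1.402-1.96) = 81.4%.

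This agrees with 80% and shows that the SAP's sizing carries the ICC of 0.2. A cruder design effect of 2.29 gives 77.0%. The power statement is not in dispute.

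**3. ICC on the responder scale.** A latent ICC of 0.2 with 30% responders gives a responder-scale ICC of 0.119.

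**4. Analytic check of ignoring group, one visit.** Design effect D = 1+((1+CV^2)m-1) x ICC; actual alpha = 2(1-Phi(1.96/sqrt(D))).
- m = 4, CV 0: D = 1+3(0.119) = 1.36, alpha 9.2%.
- m = 4, CV 0.7: D = 1+4.96(0.119) = 1.59, alpha 12.0%.

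**5. Null simulations of the planned analysis.** Three visits, arm-by-visit terms, exchangeable logistic GEE, 3-month contrast, 14 vs 7 groups of mean size 5, CV 0.7, 20% missing, 30% responders. Three separate sets of runs were made, with 547-600, 1,500 and 4,000 replicates per setting. Rejection rates at nominal 5%:

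| Unit and variance | ICC 0 | latent ICC 0.05 | latent ICC 0.2 |
|---|---|---|---|
| Participant, robust | 4.7-4.9% | 4.8-6.2% | 10.4-11.0% |
| Group, plain robust | about 8-10% | about 8-10% | about 8-10% |

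Over all settings at CV 0.7, the group rows were 7.7-8.5% in the 547-600-replicate set, 8.2-9.1% in the 4,000-replicate set and 8.6-9.9% in the 1,500-replicate set. In the 4,000-replicate set, smaller size variation gave 7.8% at CV 0.5 and 7.7% at CV 0. The Monte Carlo standard error near 9% is sqrt(0.09 x 0.91/1,500) = 0.7 points for 1,500 replicates and 0.5 for 4,000.

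If the ICC were about 0.19 on the responder scale itself (1,200 replicates), participant as unit gave 13.4% and group plain robust 8.7%.

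**6. The remedy.** Group as unit, Mancl-DeRouen variance, t on 21-2 = 19 df: 2.8-3.9% for the odds ratio and 4.7-6.1% for the risk difference.

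**7. Odds ratio against difference.** p1 = OR x p0/(1-p0+OR x p0). With OR = 2 and an assumed control rate of 10%, p1-p0 = 0.182-0.100 = 8.2 points. With a control rate of 40% it is 0.571-0.400 = 17.1 points. The same odds ratio therefore leaves the named quantity open by a factor of about two.

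**The case against.** **Participant may be the intended unit.** It matches the participant random effect in the primary model (SAP 5.2), and the small-sample issue then largely disappears. The SAP calls 0.2 conservative and expects no strong group effects. This stands: near ICC 0 the participant reading is about nominal. A reader might infer that the analysis is invalid however it is read, and the documents do not support that. They also do not establish that the ICC is near 0, since the SAP sized the trial at 0.2 and plans a group-level check for the primary outcome.

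**The inflation for group as unit can be overstated.** A single-visit simulation at CV 0.7 gives 10-12%, and a reader might take that as the size. The SAP analyses three visits, and there the figure is about 8-10%. CV 0.7 is also the top of the SAP's range.

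**The remedy may be heavier than the odds ratio needs.** This is partly right: in the 547-1,200-replicate runs a bias-reduced variance with a plain normal reference already gave 4.0-5.5% for the odds ratio. The Mancl-DeRouen variance with t earns its place for the risk difference, where a milder (Kauermann-Carroll) correction with the same t still rejected at 7-9% at CV 0.7 in single-visit runs.

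**The odds ratio tests the same null, and a difference can be derived from the same model.** Both are true, but the SAP does not plan that derivation; section 3.1 promises intervals for mean differences only.

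**Published code may settle the unit.** It would if it covers this analysis. It would not by itself correct the variance or supply the risk difference.

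**Conclusion.** The point holds as a should-fix item on a secondary outcome. Section 5.3 leaves the clustering unit open, and the consequence depends on the reading. With group as unit and no correction, the test runs at about 8-10% at any ICC. With participant as unit, it is about nominal at ICC 0, about 5-6% at latent ICC 0.05 and about 10-11% at 0.2. Intervals can therefore be too narrow under either reading, but under the participant reading only if the ICC is clearly above zero. The mismatch between the defined difference in proportions and the planned odds ratio stands whatever the ICC.

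The sizes rest on 30% responders, 14 vs 7 groups, CV 0.7, 20% missing and an ISI-scale ICC carried over to improvement. A reader might extend this to the trial's main result. It does not reach that far, because the primary outcome is continuous ISI in a separate model.

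**What to change.** In SAP 5.3:

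1. Name rehabilitation group as the GEE clustering unit, with all visits of all members in one cluster and arm-by-visit terms. Use a Mancl-DeRouen type bias-corrected robust variance and a t reference on number of groups minus 2 df.
2. Report the marginal risk difference with 95% CI at 3, 6 and 12 months, with the odds ratio alongside.
3. State in 3.4.2 that the code published in advance includes this analysis.

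The SAP already foresees an updated version before unblinding (section 5.2), which can carry the change. The cost is a few sentences and some code. The checks here were run in Python and the SAP specifies Stata, so the team should confirm how the corrected variance will be obtained there.

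The statistical price is somewhat wider intervals. In single-visit runs at 30% responders, the risk-difference interval was 11-16% wider than with participant as unit if the true ICC is 0, and 30-43% wider at ICC 0.2, where the narrower interval is too short. The odds-ratio test becomes mildly conservative, at about 3-4%.

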## 5.4 Pre-planned exploratory analyses

We plan to conduct exploratory analyses identifying whether changes in pain intensity and fatigue mediate the effect of dCBT- I on insomnia severity. Likewise, we will identify whether changes in insomnia symptoms and fatigue mediate the effect on pain severity. We will follow the international, consensus-based guidance for the reporting of mediation analyses of randomized trials. If the data material allows the analyses above to be conducted, the results will be published in an additional publication.

## 5.5 Statistical software

All analyses will be done using StataMP 18 (StataCorp. 2023. *Stata Statistical Software: Release 18*. College Station, TX: StataCorp LLC).

